### 3.3. C. Research Design and Methods: R61 Phase.

**3.3. C.1. Overview.** The R61 Phase is designed to clarify engagement of the attention allocation target, to optimize dosage of GC-MRT (RCT comparing 8 vs. 12 sessions), and to explore whether the treatment engages two processes influencing attention allocation: disengagement from threat, and social reward.

**3.3. C.2. R61 Method: Patients:** The goal is to enroll a sample with clinically significant SAD, using few exclusion criteria to maximize generalizability. Patients will be obtained by clinical referral and recruitment notices posted online and locally. Forty adults age 18-60 with clinically significant SAD, as assessed by MINI structured interview and self-rated Liebowitz Social Anxiety Scale (LSAS-SR) total  $\geq 50$ , will enter the study after psychiatric clinical evaluation, including and Hamilton Rating Scale for Depression (HRSD). The LSAS cutoff score was chosen for optimal balance between diagnostic specificity and sensitivity for SAD. Key exclusion criteria will be at least moderately severe depression (HDRS 17-item score  $>20$ ), indicating greater need for non-experimental treatment; substance use disorder in the past 30 days (other than nicotine, or mild alcohol or cannabis abuse); bipolar or psychotic disorders; acute suicidal ideation (assessed by Columbia Suicide Severity Rating scale, CSSR); other unstable psychiatric, neurological, or medical conditions that could interfere with study participation or interpretation of outcomes; contraindication to MRI. (see Human Subjects for details).

[figure not shown]
The self-rated version of the LSAS will be used only at screening for eligibility assessment. The clinician-rated LSAS will be the primary outcome measure, assessed at baseline, during treatment, and post-treatment. Using the self-rated LSAS at screening avoids the bias that reportedly can occur when the primary outcome measure is the basis for an entry cutoff criterion, as raters could feel pressured to maximize baseline scores to meet the cutoff, thus distorting outcomes.

**3.3. C.3 R61 Intervention:** Patients will be randomized to 8 biweekly sessions of GC-MRT over 4 weeks vs. 12 sessions of GC-MRT over 8 weeks (8 biweekly, then 4 weekly), using GC-MRT as described above in the preliminary study, but without a control treatment – all R61 patients will receive active GC-MRT.

Training sessions of 20 min. will use the Eye-Link 1000 plus eye-tracker running Experiment Builder software (SR Research, Kanata, Ontario, Canada). Before each training session patients will be told that background music will accompany the session. Staff will provide a music menu and ask the patient to choose music he or she would like to hear during the session. Each training session begins with a 9-point gaze calibration, followed by 9-point validation, yielding reference data needed for computing gaze positions. Calibration will be repeated if visual deviation is  $>0.5$  degrees on the X or Y axis, and training will begin only when calibration parameters are achieved. Operating distance to the eye-tracking monitor will be 70 cm. The stimuli will be presented on a monitor with 1920 $\times$ 1080 pixel resolution. Patients will be asked to view each face matrix freely in any way they choose, without additional instruction. GC-MRT group patients who inquire about the interruptions in music will be told that everything is working properly and to continue to view the stimuli. Independent evaluators will not be aware of session-scheduling nor observe training sessions, which will be held in a remote room. Patients will be told to refrain from discussing their training session experiences during clinical assessments.

### 3.3. C.4 Assessments :

These will include eye tracking of attention allocation during GC-MRT, self-ratings, clinician ratings (by an independent evaluator blind to GC-MRT dose assignment and scheduling of GC-MRT sessions), computer-based behavioral tasks, and MRI. Attention allocation will be assessed at every GC-MRT session. MRI assessments and behavioral tasks will be conducted pre- and post-treatment. All other outcome assessments will be conducted at baseline and at weeks 2, 4, and 8, and 3 months later (3-month follow-up).

**3.3. C.4.a. Primary Outcome Assessment for Target of Attention Allocation:** The primary outcome measure will be defined as % dwell time on threat faces (dwell time on threat faces/dwell time on all faces), derived from eye-tracking data obtained throughout each treatment session. Fixations will be defined as  $\geq 100$  ms of stable fixation within  $1^\circ$  visual angle. For each matrix we will define two Areas of Interest (AOI's), one of the eight disgust facial expressions (i.e., the threat AOI) and one of the eight neutral facial expressions (the neutral AOI). Attention allocation to threat will be measured by computing total dwell time in milliseconds per defined AOI and calculating the proportion of dwell time on the threat AOI relative to total dwell time on both AOI's, thus reflecting gaze allocation to threat stimuli. Percentage of dwell time on threat AOI across the 30 presented matrices for each session will be averaged for a final score of attention allocation to threat per session. As in the pilot study, to derive baseline % dwell time we will average the percentage of dwell time on threat AOI during the first five matrices presented in Session 1, as gaze-contingency learning has been shown to be minimal at this early stage.

**3.3. C.4.b. fMRI Tasks:** Patients will complete MRI twice (pre-treatment and post-treatment) using tasks that have been previously shown to differentiate SAD from control participants. Resting state data will be obtained for 15 minutes prior to task completion.

**Attention control task:** The Emotional Faces Shifting Attention task (EFSAT) will be used to assess distraction of attention by threat faces. EFSAT stimuli are comprised of a trio of geometric shapes (circles, rectangles, triangles) alongside a trio of faces within the same field of view. For "Match Faces," participants select one of two bottom faces (neutral vs. emotional) matching the emotion of the top target face. "Match Shapes" will have similar instructions, to select one of two bottom shapes that matches the top shape. Face stimuli are from a validated stimulus set, the identities always differ, and equal numbers of male and female faces are presented. The paradigm comprises 36 blocks: 18 blocks of matching shapes interleaved with 18 blocks of matching emotional faces, counterbalanced across two runs. Each target face condition (angry, fear, happy) is presented for an entire block six times without repetition. Each 20s "task" block contains four sequential matching trials, 4s each, preceded by a 4s instruction image to either "Match Faces" (attend to faces) or "Match Shapes" (attend away from faces). Participants respond by pressing response buttons. Stimuli will be presented using presentation software (Neurobehavioral Systems).

**Social Incentive Delay task:** This social reward version of the Monetary Incentive Delay task was developed to assess social and monetary reward processing. We will use the social reward processing runs of this task. Participants are informed that pictures of neutral faces will be presented as rewards for successful trials. Each of 3 runs are "win versions" (i.e., faces can be won or not won, but cannot be lost). Trial "wins" result in the presentation of a static image of a face with a neutral expression (closed mouth images selected from the NimStim set of facial expressions). Runs begin with a 10s instructional screen.

Each trial includes: (i) a 2000ms cue indicating whether adequately quick responses to the bulls-eye would result in a 'win' (a triangle) or not (a circle); (ii) a 2000–2500ms crosshair fixation; (iii) a target bulls-eye presented for up to 500ms that requires a speeded button press; (iv) 3000ms of feedback that indicates whether that trial is a 'win' or not, with wins accompanied by an image of a face and (v) a variable length inter-trial interval crosshair such that the total duration of each trial is 12s. Trial types (i.e., potential win or no potential win) are aperiodic and pseudorandomly ordered. Each 8 min run contains 40 trials, of which 20 are potential win trials. During each run, participants view a face image reward if responses to the bulls-eye are adequately quick. Coincident with feedback, cumulative win totals are presented. Participants will be instructed to respond to all target bulls-eyes as quickly as possible to win on as many trials as possible, and win or non-win outcomes are contingent on reaction times. The task is adaptive such that participants are successful on two-thirds of trials, regardless of individual differences in reaction times. Prior to scanning, participants rate face stimuli on the dimensions of valence and arousal. Stimuli will be presented using E-Prime presentation software version 1.1 (Psychology Software Tools Inc., Pittsburgh, PA, USA).

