### 3.3. C.4.d. Diagnostic and Clinical Rating Assessments

Raters (MD or PhD level) experienced with the assessment of SAD will conduct clinician assessments. Independent evaluators blind to randomization assignment will conduct the primary symptom severity outcome measure (LSAS) and other outcomes. Reliability will be established by joint ratings prior to study initiation and repeated at 6-month intervals during the study to minimize drift.

**MINI International Neuropsychiatric Interview** (MINI, screening only). This structured diagnostic interview will establish DSM-5 diagnoses for eligibility assessment.

**Liebowitz Social Anxiety Scale – Self-Rated** (LSAS-SR, screening only) 24-item self-rated assessment of social anxiety symptom severity, well validated.

**Hamilton Rating Scale for Depression**, 17-item (HRSD, screening and weeks 0,2,4,8, 3-month follow-up)

**Columbia Suicide Severity Scale** (screening and as-needed) will be used for screening and to assess an suicidal ideation occurring during participation.

Outcome measures at weeks 0,2,4,8, 3-month follow-up:

**Liebowitz Social Anxiety Scale – Clinician-Rated** (LSAS) Widely used and well validated 24-item assessment of severity of symptoms of SAD.

**Social Phobia Inventory (SPIN)** – Validated self-rating assessment of severity of symptoms of SAD.

**Quality of Life Enjoyment and Satisfaction Questionnaire (QLESQ)** – Self-rated scale for quality of life.

**Revised Social Anhedonia Scale** – 15-item self-rated scale derived from Chapman Social Anhedonia Scale, with superior discrimination of social anhedonia from social anxiety.

**Post-treatment Debriefing Questionnaire** – This self-rated form will assess the participant's experience of GC-MRT, including treatment acceptability (using a modified version of the **Client Satisfaction**

**Questionnaire**), and awareness of the reward contingency.

**Randomization Method (R61 and R33).** We will use stratified randomization to assign subjects into two randomized groups. Strata will be defined based on baseline medication use (yes/no). Forty subjects will be randomized in the R61 phase to two dosage groups,

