**R61 Go-Nogo Criterion:** Mean % dwell time on threat faces during the last session of the 8-session or 12-session treatment will decrease by more than 7.2 percentage points relative to baseline, corresponding to a medium effect size of Cohen's  $d=0.48$ , based on preliminary data. We have  $>80\%$  power to detect this difference under all scenarios. Clinical significance of cutoff: Based on preliminary data, since % dwell time reduction will partially mediate clinical symptom reduction, this effect corresponds to symptom reduction of  $d = 1.34$ , corresponding to 21.3 points on the LSAS scale. **R61 criterion for selecting dose for the R33:** If only one dosage group passes the Go-Nogo Criterion, that dose will be selected for the R33. If both dosage groups satisfy the Go-Nogo Criterion, we will decide based on the following: If improvement (decrease) in LSAS total score 8 weeks after starting treatment is at least 7 points greater in the 12-session/8-week treatment group than in the 8-session/ 4-week treatment group, we will use the 8-session/12-week treatment in the R33.

**Aim 4: Hypothesis 3:** *Compared to control treatment, GC-MRT will significantly improve symptoms (LSAS) & QoL (Quality of Life Enjoyment & Satisfaction Scale, QLESQ: a) at post-treatment and b) at 3-month follow-up.* As primary analysis, we will use a two-sample t-test for the LSAS change scores at the last session in completer subjects. For the 3-month follow-up, a similar analysis will be performed. Secondary analysis will be similar analyses of the QLESQ, and a mixed effects model of each outcome with change score (relative to baseline) as the outcome, and randomization group, time point, and the baseline score as the predictors. Power Analysis. We assume 10% drop-out in each group. From our preliminary data analysis, expected effect size for reduction in LSAS for completer subjects, compared to controls, will be  $d = 1.35$ . Using a two-sample t-test, with Bonferroni-corrected 0.025 significance level, we will have 99% power to detect this. We do not have preliminary data for the QLESQ; the minimal detectable effect size for the change difference will be  $d=0.74$ , a moderate effect size.

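### R61 target engagement sets a five-matrix Session 1 baseline against 30-matrix training means, so a within-session response that does not carry over would count as a fall in % dwell time

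*Combined protocol and SAP*

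**What the plan says.** The measure is defined in section 3.3. C.4.a. It is "derived from eye-tracking data obtained throughout each treatment session", so it is recorded while training is running. For session scores, "Percentage of dwell time on threat AOI across the 30 presented matrices for each session will be averaged for a final score". For baseline, "we will average the percentage of dwell time on threat AOI during the first five matrices presented in Session 1, as gaze-contingency learning"; the reason offered is that such learning "has been shown to be minimal at this early stage". The plan adds that the pilot study derived baseline in the same way.

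Section 3.3. C.3 states that R61 gives GC-MRT to everyone, "but without a control treatment". The description of the training sessions that follows shows that music is interrupted during them: "GC-MRT group patients who inquire about the interruptions in music will be told that everything is working properly".

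Two decisions use the contrast (section 3.3. C.5). The primary analysis of Hypothesis 1 models change from this baseline over all sessions after session 3 and tests the pooled intercept. The R61 Go-Nogo Criterion reads "Mean % dwell time on threat faces during the last session of the 8-session or 12-session treatment will decrease by more than 7.2 percentage points", with the Session 1 baseline as its reference. A secondary analysis uses all sessions with categorical time. The debriefing questionnaire in section 3.3. C.4.d records "awareness of the reward contingency", but no dwell-time analysis uses that item.

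**The concern.** The reason given for stopping the baseline at matrix 5 is that little contingency learning has occurred by then. This allows for dwell time to shift later in the same session. The baseline leaves that later window out, yet 25 of the 30 matrices in every follow-up score fall inside it.

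Suppose a patient relearns the contingency in each session and starts the next one with attention unchanged. That patient's 30-matrix mean lies below the five-matrix baseline every time. Session 1 would show the same fall against its own first five matrices, before anything could carry over. Starting the primary analysis after session 3 does not remove the mismatch, because it recurs in every session. There is no control arm to subtract it.

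At stake is the meaning of a Go. R61 is meant to clarify engagement of the attention-allocation target, and its gate governs progress to R33 and can select the dose. As scored, the contrast cannot separate change retained between sessions from a response to the contingency while it is active.

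**Working it through.** **1. The plan's own figures.** Inputs from section 3.3. C.5: 40 enrolled, 10% dropout (36 completers, 18 per dose group), alpha 0.05, expected d = 0.68, minimum detectable d = 0.48, threshold 7.2 points. The plan does not state sidedness; two-sided is assumed. An exact noncentral-t calculation for a paired t-test with n = 36 gives:

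- power at d = 0.68 of 97.8% (plan: at least 98%);
- power at d = 0.48 of 80.0%, so the 80% minimum detectable d is 0.480 (plan: 0.48).

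These reproduce. The power arithmetic is not in question; what the contrast measures is. The implied SD of change is 7.2 / 0.48 = 15 points, and the expected fall is 0.68 × 15 = 10.2 points.

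**2. Contrast under no carry-over.** Let every session repeat one within-session curve. Then

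apparent fall = (mean fall over matrices 1-30) − (mean fall over matrices 1-5).

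A like-for-like contrast (first five against first five, or 30 against 30) has expected value 0. For the planned contrast, with D the drop (the end-of-session drop for the linear curve, the asymptotic drop for the exponentials):

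| Assumed curve | Apparent fall | D giving 7.2 | D giving 10.2 |
|---|---|---|---|
| Step after matrix 5 | 25/30 × D = 0.833 D | 8.64 | 12.24 |
| Exponential, time constant 5 matrices | 0.514 D | 14.0 | 19.8 |
| Exponential, time constant 10 matrices | 0.494 D | 14.6 | 20.6 |
| Linear, matrices 1-30 | (14.5/29 − 2/29) × D = 0.431 D | 16.7 | 23.7 |

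Neither D nor the curve is in the documents. The step is the shape that needs the smallest drop.

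**3. Chance of passing the gate with nothing retained.** This uses the step curve, a normal approximation, SD 15 and n = 18 per dose, so the standard error is 15/√18 = 3.54. P(Go) per dose = 1 − Φ((7.2 − 0.833 D)/3.54). For at least one of two doses it is 1 − (1 − P)².

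| D | Apparent fall | P(Go), one dose | P(at least one dose) |
|---|---|---|---|
| 0 | 0 | 2% | 4% |
| 5 | 4.17 | 20% | 35% |
| 8.64 | 7.20 | 50% | 75% |
| 10 | 8.33 | 63% | 86% |
| 12 | 10.00 | 79% | 95% |

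The row D = 0 is also what a like-for-like contrast with the same SD would give at any D. The other curves give smaller probabilities at the same D, because their multipliers are smaller.

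**4. What the all-session analysis would show.** If Session 1's own 30-matrix score enters as a time point, a profile that is flat from Session 1 onward would point to no carry-over. But the analysis tests each time point against the five-matrix baseline, not against Session 1. A profile that declines over sessions could also come from faster relearning within each session. Exposure is therefore partial, and the result enters neither the primary test nor the gate.

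**The case against.** Hypothesis 1 says only that dwell on threat will fall during GC-MRT, and the outcome is openly defined from training data. On that reading a response during training is the target, and retention is an extra demand. This stands as far as the wording of Hypothesis 1 goes. However, the plan also treats dwell reduction as a partial mediator of symptom reduction (R61 Go-Nogo Criterion) and expects it to be associated with LSAS and QLESQ improvement at 3-month follow-up (Hypothesis 4). Both uses are easier to defend if the change outlasts the session.

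The baseline is sound as a pre-learning value, and keeping the pilot's scoring keeps the 7.2-point cutoff comparable with its source. Both points stand, and they are reasons to leave the criterion on its present measure. The preliminary-study description is not in the supplied text, so within-session curves or a contingency-free assessment may be reported there. The outcome in section 3.3. C.4.a uses neither.

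Three stronger readings are tempting but unsupported:

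- *The effect does not persist, so a Go would be false.* The documents say only that learning is minimal in the first five matrices of Session 1. They do not say that it completes within a session or is lost between sessions.
- *A drop of under 9 points is enough to pass.* That holds only for an immediate step after matrix 5, a shape no document supports.
- *The gate should also require a fall in the first-five score.* With nothing retained and symmetric error, a bare mean decrease would occur about half the time. Nor is the first-five window at later sessions described as contingency-free: a patient who has noticed the rule could look at neutral faces from matrix 1.

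**Conclusion.** The point holds as a limit on interpretation. The Hypothesis 1 contrast and the Go/No-Go gate compare unlike windows, and a response with no carry-over between sessions would register as a fall in both. The drop needed to reach 7.2 points ranges from 8.64 (step) through 14.0-14.6 (exponential) to 16.7 (linear).

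These figures assume no carry-over at all and the same curve in every session. The pass probabilities further assume the step curve and the implied SD of 15. The documents do not settle whether any of this occurs; the Session 1 recordings can estimate the size and shape of the curve. The conclusion is that the plan as scored cannot tell retained change from response during training, not that retained change is absent. A supporting analysis is warranted; a changed gate is not established.

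**What to change.** Keep the 7.2-point criterion on its present measure. Before the dwell-time data are analysed, pre-specify a key supporting analysis from the recordings already made:

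1. Change in mean % dwell time over matrices 1-5, last session minus Session 1, and over the sessions after session 3 minus Session 1, each with a 95% confidence interval.
2. Beside it, the Session 1 within-session drop: mean of matrices 6-30 minus mean of matrices 1-5.
3. The contrast in item 1 repeated descriptively in patients unaware of the contingency at debriefing.
4. All of these reported with the Go/No-Go result, and any claim of retained change in attention allocation limited to what the first-five contrast supports.

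The cost is re-scoring and a short addition to section 3.3. C.5; no new assessment is needed. The main downside is precision. Even at SD 15 the 95% half-width for the last-session contrast would be about 2.03 × 15/√36 = 5.1 points pooled and 2.11 × 15/√18 = 7.5 points per dose. A five-matrix follow-up score is noisier than a 30-matrix one, so the real intervals are likely to be wider. The unaware subset is of unknown size. Patients aware of the contingency may shift gaze from matrix 1, so this is supporting evidence and not a hard gate.

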### 3.3. C.4.c. Behavioral Task Assessments

**Attention Control Task:** (see EFSAT 3.3. C.4.c. above) This will assess reaction times for matching shapes alongside happy versus angry distractors.

**Probabilistic Social Reward Learning Task:** This 25-min task is presented using E-Prime (version 1.1; Psychology Software Tools, Inc, Pittsburgh, PA). Subjects press a button to indicate whether a short (11.5 mm) or a long (13 mm) mouth appeared on a previously mouthless cartoon face. The task includes three blocks of 100 trials. Within each block, an equal number of short and long mouths appear for 100 ms each. The difference between mouth sizes as well as the duration of stimulus exposure is small, providing an ideal experimental setting for a response bias to develop without risk of inducing performance at chance level.

Using an asymmetric reinforcer ratio elicits a response bias. Correct identification of either the short or long mouth is rewarded (by a video clip of smiling actor with thumbs up sign) three times more frequently ("rich stimulus") than correct identification of the other mouth ("lean stimulus"). The reinforcement allocation and key presses are counterbalanced across subjects. In each block, only 40 correct trials (30 rich, 10 lean) are

rewarded, so each subject is exposed to the same reward ratio. Subjects are informed that the purpose of this task is to win as much money as possible, and that not all correct response will receive a reward feedback; but they will be unaware of the disproportionate reward for one of the stimuli.

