corresponding to  $d = 0.34$ , while with  $r = 0.2$ , the minimal detectable effect size is  $f = 0.23$  or  $d = 0.45$ . In either case, the power for  $d = 0.68$  will be  $>99\%$ .

**Aim 2: Hypothesis 2:** *Eight weeks after starting treatment, mean Liebowitz Social Anxiety Scale (LSAS) total score will be significantly lower in the 8-week treatment group than in the 4-week group.* We will use a t-test for the change score at 8 weeks after starting treatment for completers. We will also compare groups on % dwell time at last session but do not expect a group difference. Power Analysis. We do not have preliminary data for the 8-week dose of treatment. For the two-group t-test, with  $n=20$  per group enrolled, and 18 per group completers (10% dropout), we will have 80% power to detect an effect of size  $d=0.96$  or larger. Thus we will be able to detect large effect sizes for the dosage difference. However, dose selection for the R33 will not require statistically significant superiority (see criterion for selecting dose, below).

**Aim 3 (Exploratory):** (See below for processing MRI and tasks data) We will test the association between change in attention control and reward processing and change in % dwell time by Pearson correlation coefficients. *We will also explore predictors of target engagement (baseline attention allocation and neural activation), to advance personalized treatment.* We will fit mixed effect regression models as described in Hyp 1, with repeatedly measured reduction in % dwell time as outcomes, with the predictors listed above.

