Reward Task behavioral analysis: Valence, arousal ratings of faces, and reaction times (RTs) for both potential reward and non-potential reward trials will be recorded. RTs, valence and arousal ratings of faces will be submitted to 2-way t-tests (pre-, post-treatment) for the R61 phase for each dose group. For the R33 phase, a two-way ANOVA will be conducted to test main effects of Group (control and treatment), Time (pre- and post-treatment), and Group by Time interactions. Interactions will be followed up with two-tailed t-tests,  $p < 0.05$ .

Social Probabilistic Reward Task: Response bias ( $\log b$ ; primary variable) and discriminability ( $\log d$ ; control variable) will be computed following prior procedures. using the following formulas:

$$\log b = \frac{1}{2} \log \left( \frac{Rich_{correct} * Lean_{incorrect}}{Rich_{incorrect} * Lean_{correct}} \right) \quad \log d = \frac{1}{2} \log \left( \frac{Rich_{correct} * Lean_{correct}}{Rich_{incorrect} * Lean_{incorrect}} \right)$$

Response bias indexes the systematic preference for the response paired with the more frequent reward ("rich stimulus"), or the extent to which behavior is modulated by reinforcement history. A high response bias emerges when subjects show high rates of correct identification (hits) for the rich stimulus and high miss rates for the lean stimulus (i.e., the stimulus associated with less frequent rewards). To examine general task performance, secondary analyses will consider hit rates scores (% correct responses), RT, and discriminability. Discriminability assesses the subjects' ability to perceptually distinguish between the two stimuli, and thus can be used as a proxy of task difficulty.

Data Reduction: The main dependent variable for the PRT will be Reward Learning, operationalized as the increase in response bias during the final block relative to the first block [Reward Learning =  $\Delta$ Response Bias = Response Bias(Block 3) - Response Bias(Block 1)].  $\Delta$ Response Bias is consistently positive in healthy subjects, and we selected this as the main outcome measure because lower values of it have been linked to current and future anhedonic symptoms and reward-related cortico-striatal activation.

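### The social reward learning task tells participants they are playing for money, but the only reward it describes is a social video clip

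*Combined protocol and SAP*

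**What the plan says.** Section 3.3. C.1 gives as one R61 purpose to explore whether treatment engages "two processes influencing attention allocation: disengagement from threat, and social reward". One behavioral measure of the second process is the Probabilistic Social Reward Learning Task in section 3.3. C.4.c. Participants judge whether a short or a long mouth appeared on a cartoon face. Correct identification of one of the two mouths "is rewarded (by a video clip of smiling actor with thumbs up sign) three times more frequently" than correct identification of the other. On quantity: "In each block, only 40 correct trials (30 rich, 10 lean) are" rewarded.

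On what participants are told, the same description says they are informed that "the purpose of this task is to win as much money as possible". They are also told that not every correct response brings reward feedback.

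Section 3.3. C.5 defines response bias and then says: "The main dependent variable for the PRT will be Reward Learning", meaning response bias in block 3 minus response bias in block 1. For Aim 3, labelled exploratory, the plan is: "We will test the association between change in attention control and reward processing and change in % dwell time by Pearson correlation coefficients". Aim 5, also exploratory, uses the same assessment methods to relate reward processing to symptom change.

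**The concern.** The stated goal is money and the described reward is social approval. A participant who believes the instruction may treat the clip as a sign that money has been earned. Someone indifferent to social approval could then still learn to favor the richer stimulus. The score would be read as social reward sensitivity although part of it came from a monetary motive.

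What is at stake is the interpretation of a mechanistic measure. A correlation between change in this score and change in % dwell time, or its absence, could not be attributed to social reward with confidence. The problem cannot be repaired in the analysis once data are collected, because nothing recorded in the task separates the two motives.

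**Working it through.** The plan states no figure for this point, so the check is mainly a comparison of texts.

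**1. Instruction against reinforcer (section 3.3. C.4.c).**
- Task name: social reward.
- Reinforcer described: the smiling-actor clip.
- Goal told to participants: money.

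The name and the reinforcer agree; the instruction does not fit them.

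**2. Is money described anywhere else?** The only payment mentioned is remuneration for taking part, under Informed Consent in the human subjects section. It is not tied to task performance. Nothing reconciles the instruction with the clip.

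**3. How the plan handles the companion task (section 3.3. C.4.b).** The Social Incentive Delay task is described as able to assess both social and monetary reward. The plan uses only its social runs and tells participants that faces are the reward. There the two kinds of reward are kept apart and the instruction matches what is delivered.

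**4. Reinforcement schedule.** 30 rich + 10 lean = 40 rewarded trials per block, and 30 / 10 = 3, which agrees with the stated ratio. Over three blocks this is 3 × 40 = 120 rewarded trials per administration. Section 3.3. C.4 places behavioral tasks pre- and post-treatment, so 2 × 120 = 240 per participant. The schedule is internally consistent; only the instruction is at issue.

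**5. Can the score separate the motives?** Section 3.3. C.5 gives

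log b = ½ log[(Rich_correct × Lean_incorrect) / (Rich_incorrect × Lean_correct)].

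This uses only counts of correct and incorrect responses. Equal counts give equal log b whatever the motive. Discriminability (log d) controls for perceptual difficulty, not for motive.

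**6. Do the difference scores remove the problem?** As an illustration, assume bias in block k is the sum of a social part s_k and a monetary part m_k. Then

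Reward Learning = (s_3 − s_1) + (m_3 − m_1).

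A monetary part that is constant across blocks cancels. A monetary part that grows with learning does not. In the pre-to-post change, the term (m_3 − m_1) cancels if it is the same at both administrations, and otherwise remains. A score used at a single time point keeps it in full. The documents give no values for these terms, so neither size nor direction can be computed.

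**The case against.** The strongest reply is that this is a drafting slip. The title, the reinforcer and the companion task all point to social reward, and the monetary sentence may have come from a monetary form of the task. If so, no participant hears it and the validity argument falls away. The documents do not settle this. What stands is that the wording may be an error; what does not follow is that it can be left. It is written as an instruction to participants, and staff following the protocol would give it.

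Second, the absence of payment is inferred from silence. The task script and payment details are not in the documents. This is correct, and the point rests only on what is described.

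Third, a reader might infer that the score would no longer reflect social reward at all. The documents do not support that. The clip is still the reinforcer described as delivered at 3:1, so a social component remains; the instruction could add to it or mix with it.

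Fourth, a reader might infer that participants discover at the first administration that no money follows, making pre- and post-treatment scores non-comparable. That needs three things: no payment, participants noticing, and a change in their later responding. The documents show none of them. An instruction common to everyone does not by itself create a pre-post or between-arm difference.

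Fifth, Reward Learning is the main variable of this task, not of the trial. Reward processing is also assessed by the Social Incentive Delay task, through imaging, reaction times and face ratings. This stands and limits the importance of the point.

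**Conclusion.** The inconsistency is real. The plan describes a social reinforcer and a monetary instruction in the same task and does not reconcile them. If the instruction is given as written, response bias and Reward Learning may mix monetary with social motivation and would not cleanly index social reward.

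The mismatch would apply to every participant given that instruction, at both administrations, but its size and direction are unknown. Two assumptions carry the conclusion: that the sentence reflects what participants will be told, and that participants act on it to some degree.

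The consequence is confined to the exploratory reward-processing analyses in Aims 3 and 5. The % dwell time and LSAS outcomes, the Go-Nogo criterion, the dose-selection rule and all power figures are untouched. The point merits a correction because the remedy is small and the problem cannot be undone for participants already tested. It is not a threat to the trial's main conclusions.

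**What to change.** Before testing starts, replace the monetary wording in section 3.3. C.4.c and in the task script with an instruction that refers to the clip, for example to obtain as much positive feedback as possible. Use identical wording at pre- and post-treatment. Any wording chosen should be checked against the procedure on which the task is based.

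If money is in fact paid, state this and how it depends on performance, and interpret Reward Learning as a response to mixed social and monetary reward.

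If testing has already begun, report the instruction actually used and keep it constant. Changing it between a participant's two administrations would itself make them non-comparable.

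The cost is one sentence in the protocol and one in the script. Sample size, schedule and analysis do not change.
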